### 5.2 EXCLUSION CRITERIA

1. Member of the study team
2. Prescriptions written in Emergency Department or hospital setting (including upon discharge)
3. Prescriptions written in a skilled nursing facility or other institutionalized setting.

The reason for the exclusions for #2 and #3 is because these prescribers typically do not follow patients longitudinally and therefore are not eligible to receive notifications when new medication prescribing issues develop *after* the initial prescription is written.

### 5.3 SCREEN FAILURES

N/A

### 5.4 STRATEGIES FOR RECRUITMENT AND RETENTION

All prescribers using MiChart will be included in the observational data portion of the study. For the randomized trial, any prescriber of a DOAC medication will be considered for recruitment. Prescribers, not patients, are the primary subjects of this study.

Prescribers will be recruited through a message sent to MiChart users (prescribers) at least 1 week before being enrolled, as part of the regularly occurring messages to MiChart users regarding important changes and updates to MiChart.

The message will describe the protocol, and include a link to the IRB-approved consent form. It will also inform prescribers about how to "opt-out" of the protocol by replying to the email. Any prescriber who does not "opt-out" will be included in the study through a waiver of documented informed consent as approved by the IRB. All potential participants will be contacted. Only those who prescribe an anticoagulant in a manner that triggers a medication alert will be "enrolled."

Prescribers' participation will consist of receiving medication error alerts through MiChart as appropriate. The specific alert they receive will be randomly assigned. Note: all alerts will contain the same valid and clinically relevant warning about a potential prescribing error, and the alert will vary only as to whether or not there is a link/button to automatically consult a pharmacist. Similarly, notifications of an existing prescription (longitudinal) that triggers a medication alert will be routed initially to a pharmacist or initially to the prescriber's MiChart inbox..

## 6 STUDY INTERVENTION

### 6.1 STUDY INTERVENTION(S) ADMINISTRATION

#### 6.1.1 STUDY INTERVENTION DESCRIPTION

The intervention consists of an EHR alert that is presented to prescribers at the time that they are prescribing a DOAC, OR a notification in the EHR that indicates that an existing prescription for a DOAC does not meet the prescribing guidelines (a potential medication error). Existing prescription notifications are triggered once daily through an EHR registry that is updated continuously.

The **alerts** were designed through a user-centered design process to ensure that they are clear and usable. There will be two versions of the alerts that are identical other than except for one aspect: One alert will include a 'button' to click to automatically get a pharmacy consult; one will not include such a button.

The **notifications** were designed through a user-centered design process to ensure that they are clear and usable. Alerts will be identical, but will be routed one of two ways:

1. They will be routed initially to a pharmacist, who may then contact the prescriber to request/recommend a prescription change.
2. They will be routed directly to the prescriber, who may change the prescription, contact a pharmacist, or opt to keep the prescription unchanged.

#### 6.1.2 ADMINISTRATION

Alerts and notificaitons will fire through automated mechanisms using best practice advisory logic and registries in the EHR, and therefore will not require intervention from the research coordinator to function properly.

The PIs will monitor announcements from the FDA regarding the drugs apixaban and rivaroxaban for announcements and label changes to ensure that alerts and notifications adhere to up-to-date guidance. Members of the study team and steering committee also help to lead the Michigan Medicine Anticoagulation Pharmacy and Therapeutics subcommittee on anticoagulation and will ensure harmonization between institutional prescribing protocols and those used in this study.

Opt-out requests will be processed by the research coordinator and relevant study team members within 7 days of the request. Upon receipt, the requesting prescriber will be entered into the EHR database such that all study-related alerts and notifications will be suppressed. Usual care activities will not be impacted if a prescriber opts out of the study alerts and notifications.

Other than changes in participation (opt out) and changes in FDA guidance regarding the relevant medication, administration of this research will be conducted through the EHR (MiChart). No direct contact between the study team and the participants is anticipated.

## 6.2 ACQUISITION AND ACCOUNTABILITY

N/A – No devices will be acquired.

## 6.3 MEASURES TO MINIMIZE BIAS: RANDOMIZATION AND BLINDING

Participants will be randomized by computer based solely on the sampling algorithm, so unintended selection bias by the study team will not be a factor. The randomization algorithm will stratify by:

1. Trainee vs non-trainee specialist vs non-trainee pcip
2. Alert vs notification

This clinical trial is not fully blinded. Participants randomized to the different alert and notification conditions and will be blinded to the specifics of their assignment. However, they may be able to discern which condition they have been assigned to owing to the specifics of the alerts and notifications they receive. During the data analysis, study team members will be blinded to the alert and notification condition of the participants.

## 6.4 STUDY INTERVENTION COMPLIANCE

There are no discrete participant-initiated activities associated with participation in this protocol, so compliance is not an issue. Participants will receive alerts or notifications generated by the EHR, based on their routine clinical prescribing activities. Receipt of the notification constitutes participation and compliance. Prescribers' responses to the alerts and notifications are measured as an outcome, not as compliance.

## 7 STUDY INTERVENTION DISCONTINUATION AND PARTICIPANT DISCONTINUATION/WITHDRAWAL

### 7.1 DISCONTINUATION OF STUDY INTERVENTION

Discontinuation of a particular alerts or notification does not mean discontinuation from the study, and remaining study procedures (e.g., adverse event review) should be completed as indicated by the study protocol. If a clinically significant finding is identified after enrollment, the investigator or qualified designee will determine if any change in participant management is needed.

### 7.2 PARTICIPANT DISCONTINUATION/WITHDRAWAL FROM THE STUDY

Participants are free to withdraw from the study at any time. Data collected prior to the withdrawal may be used for analysis and publications. The study coordinator will ensure that the participant is removed from the EHR's categorization to receive alerts and notification (i.e. will no longer receive alerts and notifications) within 7 business days.

An investigator may discontinue or withdraw a participant from the study at his/her discretion. The reason for participant discontinuation or withdrawal from the study will be recorded on the study team's logs. Adverse events of special interest will be collected from the time of discharge through study completion or study withdrawal/discontinuation.

Participants who are randomized and subsequently withdraw, or are withdrawn or discontinued from the study, will not be replaced.

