#### 4.2 END OF STUDY DEFINITION

The study will end after 18 months of the alerts and notifications being active in the EHR. The duration of any individual prescriber will vary, as an individual's participation is dependent on triggering a DOAC medication alert or notification.

We will perform a one-time interim analysis after 12 months. This will asses only for safety outcomes. We will not assess for effectiveness outcomes to avoid overestimation of the effect size for effectiveness.

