### 8.3 SAFETY AND OTHER ASSESSMENTS

Participants (prescribers) will not undergo any procedures. Prescribers’ patients will be monitored for adverse events through the DSMB review.

DSMB will monitor for adverse events every 6 months. Adverse events will be measured up to 30 days after the alert or notification occurred. The safety outcomes being monitored by the DSMB include bleeding and thromboembolic events (including stroke and venous thromboembolism). These will be identified through diagnostic code searches within the EHR (see appendix A) and will undergo adjudication as described below.

Investigators will report serious adverse events in accordance with IRBMED requirements. The investigator will follow usual clinical practices at UM for reporting to regulatory authorities serious, unexpected events related to standard of care medications and devices.

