#### 8.4.2.1 SEVERITY OF EVENT

The following guidelines will be used to grade severity of AEs:

Bleeding related events, as defined by the International Society on Thrombosis and Haemostasis (ISTH):

- Major,
- clinically relevant, non major
- minor

Thrombotic (stroke and venous thromboembolism):

- There will be no severity grading of thrombotic events.

Any bleeding or new thrombotic event that occurs within 30 days of a study alert or notification will be included as an adverse event.

Serious adverse events include any death or life threatening outcome. This includes ISTH major bleeding event and any new thrombotic event that occurs within 30 days of a study alert or notification.

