### 9.3.4 ANALYSES OF IMPLEMENTATION

**Reach:** To assess reach, we will examine the proportion of patients on DOACs that had alerts or notifications fire, as well as the proportion of prescribers that received alerts and/or notifications. To further understand reach, we will also report the proportion and clinical predictors of prescribers who dismissed alerts or notifications (defined as no action within seven calendar days). We will also identify the proportion and predictors of prescribers who used anticoagulation clinic pharmacist referrals in new-prescription alerts. We will also categorize all DOAC alerts based on prescriber and patient characteristics (e.g., demographics, comorbidities).

**Effectiveness:** Analysis of Effectiveness will be the focus of the primary and secondary outcome measures (as noted above). We will evaluate the effectiveness of our DOAC alert system components by examining patient-level clinical adverse event rates (bleeding and thrombotic) within 30 days of triggering the alert. This time period was selected to minimize potential contamination from the safety review mechanism described above, and we recognize that rates for the adverse events will be low.

However, as a T4 implementation study, the primary goal is implementing the evidence-based practice for which efficacy is already established. Supplementary analyses will also examine the effect of the alert system overall on adverse events.

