Clinical adverse events assessed will include major and clinically-relevant non-major bleeding (CRNMB) events, as defined by the International Society on Thrombosis and Haemostasis (ISTH), new or recurrent VTE events, and stroke or systemic arterial embolic events objectively identified by imaging and identified as a new event by their primary clinical provider. Transient Ischemic Attacks (TIAs) that do not result in findings on imaging (such as CT or MRI) will not be included. Each of these events will be captured using health informatics tools (described below) and adjudicated every six months. Adjudication will occur at least one month prior to six month DSMB meetings to allow for the DSMB to review findings in advance of the meeting. We will use Michigan Medicine-developed health informatics tools to create a report that identifies all patients whose prescribers have received an alert or notification and any adverse event diagnosis codes within 30 days thereafter. These cases will then be reviewed by the adjudicators to determine if an adverse event occurred and if it was associated with medication management, as defined in Section 8.4.2.2. The adjudicators will have access to all laboratory and medication data as well as clinical notes, but will be blinded to group allocation. The report, created by Michigan Medicine health informatics research team, will undergo a validation process for accuracy by the study team leads, including a cardiovascular physician and pharmacist.

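### Section 7.2 ties adverse-event collection to an undefined discharge and to the prescriber's withdrawal, contradicting the 30-day patient window elsewhere; the month-18 close also leaves the last windows incomplete

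*Combined protocol and SAP*

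**What the plan says.** Section 7.2, on withdrawal of participants, sets this rule: "Adverse events of special interest will be collected from the time of discharge through study completion or study withdrawal/discontinuation". Just before it, the same section addresses only the use of data gathered before a withdrawal.

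The safety sections set a different window. Section 8.3: "Adverse events will be measured up to 30 days after the alert or notification occurred". Section 8.4.2.1: "Any bleeding or new thrombotic event that occurs within 30 days of a study alert or notification will be included as an adverse event". Section 9.3.4 describes the effectiveness analysis as "examining patient-level clinical adverse event rates (bleeding and thrombotic) within 30 days of triggering the alert", and describes an EHR report that "identifies all patients whose prescribers have received an alert or notification and any adverse event diagnosis codes within 30 days thereafter". None of these ends at withdrawal or at study closure. Section 9.2 places every randomized participant who received an intervention in the safety analyses.

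Sections 5.4 and 8.3 make clear that the study subject is the prescriber and that the events monitored are those of the prescriber's patients. The setting is ambulatory (5.1), and prescriptions written in the emergency department or hospital are excluded, discharge prescriptions among them (5.2).

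On closure, section 4.2 says: "The study will end after 18 months of the alerts and notifications being active in the EHR". The schedule of activities (1.3) puts the conclusion of data collection, and an event and DSMB review, in the 18-month column. No follow-up period after the last alert is stated.

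**The concern.** The 7.2 sentence reads as if the participant were a patient leaving hospital. Here it has two effects. Its starting point does not correspond to any study time point. Its stopping point makes a patient's safety follow-up depend on whether the clinician stays in the study, although a patient's exposure to a changed or unchanged prescription does not end when the clinician opts out.

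Three uses depend on the event count: the presentation of adverse events by randomized group and the p<0.01 trigger for halting or modification (both 9.3.6), and the check on whether the 15-day dashboard embargo contributed to harm (8.4.2.2). If staff followed 7.2 literally, the count would be incomplete for withdrawn prescribers. An extraction at month 18 would also leave the most recent alerts and notifications without a full window, for safety and for the primary outcome.

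**Working it through.** The plan gives no figure to reproduce for this point. The check is a comparison of rules, then arithmetic for scale.

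**1. The rules side by side**

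| Section | Starts at | Ends at | Depends on prescriber's status? |
|---|---|---|---|
| 7.2 | a discharge, undefined | study completion or withdrawal | Yes |
| 8.3 | alert or notification | 30 days later | No |
| 8.4.2.1 | alert or notification | 30 days later | No |
| 9.3.4, analysis | triggering of the alert | 30 days later | No |
| 9.3.4, EHR report | alert or notification | 30 days later | No |

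Section 8.1 also uses 30 days for the clinical events. The first row differs from the rest on both the start and the stop.

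**2. A test case.** A notification fires on day 0, the prescriber withdraws on day 3, and the patient bleeds on day 10. Under 7.2 collection stopped on day 3, so the event is not collected. Under 8.4.2.1, day 10 is within 30 days, so it is. Both rules cannot be followed.

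**3. Does 7.1 settle it?** Section 7.1 keeps adverse event review going when a particular alert or notification is discontinued, on the ground that this is not discontinuation from the study. Withdrawal from the study is the case it leaves out.

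**4. Windows cut at closure.** Assumption: alerts and notifications fire evenly over 18 months. Inputs: 18 months (4.2), a 30-day safety window (8.3), a 7-day primary window (8.1), and 300 prescribers × 2 patients = 600 (9.1).

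- Firing period: 18 × 30.4375 = 547.9 days.
- Incomplete 30-day window: 30 / 547.9 = 5.5%, or about 33 of 600.
- Observation time lost: the affected alerts lose 15 of 30 days on average, so 5.5% × 15/30 = 2.7%.
- Incomplete 7-day primary window: 7 / 547.9 = 1.3%, or about 8 of 600.
- Sections 9.3.1 and 9.3.2 say seven business days, which is 9 to 11 calendar days when public holidays are ignored. The share is then 9 / 547.9 = 1.6% to 11 / 547.9 = 2.0%.

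**5. What that is worth.**

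- *Events.* With the planning rates in 9.1 (1% vs 0.5%, 300 patients per arm), expected events are 300 × 0.01 + 300 × 0.005 = 4.5 per factor. At a constant hazard, closure loses 4.5 × 0.027 = 0.12 event.
- *Primary outcome.* As a worst case, suppose every notification with an incomplete primary window counted as unchanged. Both arms' proportions scale by (1 − share), so the planned 12-point difference (40% vs 52%) shrinks by 12 × 0.013 = 0.15 point, or by 12 × 0.020 = 0.24 point with the longest business-day window.

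**6. Windows cut at withdrawal.** Only windows still open at the withdrawal are affected, each by up to 30 days. The documents give no withdrawal rate, so no total can be computed.

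**The case against.** The strongest reply is that 7.2 is one stray sentence and the operative text would collect the events anyway. The EHR report in 9.3.4 starts from prescribers who have received an alert or notification and does not remove later withdrawers. Section 9.2 makes no exception for withdrawal. Section 6.1.2 describes opting out as suppression of alerts and notifications, section 8.2 still examines prescribing by clinicians who opt out, and section 9.3.1 ties primary outcome data to the patient staying in the health system. This stands. A reader might infer from 7.2 that events of withdrawn prescribers' patients are lost; the documents support only that the rules conflict. It does not make the sentence harmless, because it is the collection rule stated in the section on withdrawal.

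The scope of the sentence is also uncertain. Adverse events of special interest are never defined; section 10.3 lists only the abbreviation. Reading the term as the bleeding and thrombotic events is an assumption, though those are the events that 8.3 says are monitored. Nor can it be said that no patient has a discharge: an ambulatory patient may have an unrelated one. What holds is that no discharge is a defined study time point.

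The closure effect is small and falls on all arms at the same calendar date.

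Three further inferences are tempting and unsupported:

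- *That prescribers who withdraw were unhappy with an alert.* No reasons for withdrawal are documented.
- *That last-week notifications will be scored as unchanged.* No rule for incomplete windows is given; the figure in the working is a bound only.
- *That about 11% of alerts would lack an adjudicated window at the final DSMB review.* Section 9.3.4 says "Adjudication will occur at least one month prior to six month DSMB meetings", and 60 / 547.9 days is about 11%. But this needs a meeting exactly at month 18. The schedule gives only a column for that time, and section 10.1.6 allows additional meetings.

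**Conclusion.** The contradiction is real and should be corrected. Section 7.2 conflicts with 8.3, 8.4.2.1 and 9.3.4 on when collection starts and stops, and with 9.2 on whose data enter the safety analyses. This rests on reading the undefined term as the monitored bleeding and thrombotic events. Its effect on the event count depends on which rule staff follow and on an unknown withdrawal rate; actual loss is not shown.

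The missing follow-up after month 18 is a separate and smaller gap. If firing is even and extraction stops at month 18, it costs about 2.7% of safety observation time, roughly a tenth of an event per factor at the planning rates, and leaves 1.3% to 2.0% of primary windows incomplete. No difference between arms is shown. Neither part threatens the primary conclusion, but a safety-collection rule should not contradict the safety definition it serves.

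**What to change.** - **Section 7.2.** Reconcile it with 8.3, 8.4.2.1 and 9.3.4. State that events are collected from each alert or notification for 30 days, for every patient who triggered one, whatever the prescriber's later withdrawal or departure. Remove the reference to discharge. Either define adverse events of special interest or use the terms of 8.3.
- **Adjacent text.** Align the sentence in 7.2 on data gathered before withdrawal, and have the information sheet say that safety data on alerts already triggered are still collected after opt-out.
- **Section 4.2 and the schedule of activities.** Stop firing at month 18 and run the final EHR extraction at least 30 days later. This also completes the primary window on either the calendar-day or the business-day reading. Hold the final adjudication and DSMB review after that extraction.

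The cost is a wording amendment with IRB review and one later EHR pull, with no added patient or prescriber visits. Final data lock and the final DSMB review move by about one to two months.

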### 7.3 LOST TO FOLLOW-UP

- Participants who leave the institution or are otherwise no longer eligible to prescribe DOAC medications will be considered "lost to follow-up."
- No actions will be taken by the study team to prevent their loss to the study.
- At the end of the trial period, the study team will compare the list of enrolled prescribers against a list of potentially eligible prescribers to determine if any enrolled prescribers have left the institution. These providers status will be noted in the data. Analysis of their prescribing patterns will be included in analysis as appropriate.

## 8 STUDY ASSESSMENTS AND PROCEDURES

### 8.1 EFFICACY ASSESSMENTS

**Outcome Measurements:**

Our **primary** outcome measure (adoption) is the proportion of DOAC notifications that lead to a change in the prescription within seven days. The denominator is the total number of DOAC prescription notifications that are sent to either the prescriber or pharmacist (per randomization). The numerator is the number of DOAC notifications that result in any change to the DOAC prescription within seven days after the notification has been sent.

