## 9.3 STATISTICAL ANALYSES

### 9.3.1 GENERAL APPROACH

The main effect analyses will allow us to determine the impact of different alert- and notification types on evidence-based DOAC prescribing in both newly prescribed DOAC prescriptions and existing DOAC prescriptions in order to understand under what contexts prescriber-pharmacist collaboration is an effective implementation strategy. In both our primary and secondary outcomes, our analyses will compare the main effects of each intervention, i.e., new prescription alerts (Alerts 1 vs 2) and existing-prescription notifications (Notifications A vs B), to determine which are most effective. For both interventions, the outcome of interest will be whether the patient whose prescription triggered the alert/notification (i.e., is receiving a non-evidence based DOAC) has their prescription changed following the alert or notification.

For the primary intervention outcome (existing-prescription notifications), main effect analyses will compare the proportion of patients receiving an evidence-based DOAC prescription within seven business days following the notification between prescribers randomized to receive the notifications themselves vs. prescribers for whom notifications were sent directly to anticoagulation clinic pharmacists.

For the secondary intervention outcome (new DOAC prescription alerts), main effect analyses will compare the proportion of patients receiving an evidence-based DOAC seven business days following the notification between prescribers randomized to receive enhanced alerts vs. enhanced alerts plus pharmacist referral.

The treatment interaction will allow evaluation of whether certain alerts and notifications work better when provided in tandem.

The main outcome analysis will use mixed-effects logistic regression models to account for the binary patient-level outcome variable of evidence-based DOAC receipt after an alert. The two treatment factors and their interaction will be included as fixed effects, as well as any stratification variables and baseline patient- and/or prescriber-level characteristics that are unbalanced. A prescriber-level random effect will account for patient clustering within prescribers, and an unstructured covariance matrix will be used for residual errors. Similar mixed-effects regression analyses will be conducted for secondary outcomes, adapted for different outcome measures or levels of analysis.

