### 9.3.2 ANALYSES OF PRIMARY OUTCOMES

The primary outcome will be the number (proportion) of prescriptions triggering notifications that were changed within 7 days, among all prescriptions that triggered a notification.

As noted in the general approach, for the primary factor (existing-prescription notifications), main effect analyses will compare the proportion of DOAC prescriptions that were changed within seven business days following the notification between prescribers randomized to receive the notifications themselves vs. prescribers for whom notifications were sent directly to anticoagulation clinic pharmacists.

---

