#### **Sensitivity analyses.**

**Carryover effects for new-prescription alerts:** Primary analyses will be conducted as intent-to-treat analyses among prescriber-patient dyads for whom an alert was triggered. This allows investigation of the best types of alerts given the need for an alert. However, for new-prescription alerts, it is also possible that alerts that include the option for pharmacist referral vs. those that don't also differentially affect how many future DOAC prescribing errors are made. Specifically, prescriber-pharmacist collaboration may provide the prescriber with new knowledge about evidence-based DOAC prescribing that could be applied to future DOAC prescriptions, avoiding the occurrence of an alert altogether. To

explore these effects, we will also evaluate the main effect of the two new-prescription alerts on the proportion of DOAC patients that receive a new prescription for an evidence-based DOAC using the model described above, but including all patients to whom they prescribed a DOAC from the point they received their first new-prescription alert through the end of the 18-month study period. This will allow us to evaluate whether correct DOAC prescribing improved overall by type of new-prescription alert.

**Treatment-as-received analyses:** In line with intent-to-treat clinical best practices, prescribers will be randomized to both types of alerts at the time of their initial receipt of either type of alert. This approach was chosen for both good clinical practice and pragmatic reasons, but also with the support of our preliminary data, which showed that on one day, more than 1/4 of Michigan Medicine prescribers had one or more DOAC patients receiving a non-evidence-based prescription (see Power and Sample Size, above). There is a possibility that during trial period, some prescribers will only ever receive one type of alert, never exposed to their second randomized treatment—i.e., they made an initial prescribing error but never had a DOAC-receiving patient need a change in prescription, or vice versa. While we believe that this will be the case for only a minority of enrolled prescribers, sensitivity analyses will examine treatment-as-received effects and will re-assess main effects for the two factors including only patients for prescribers who received that type of alert.

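### The primary outcome is defined per notification, per prescription and per patient in different sections; only the per-patient version was powered, and no rule covers repeat notifications.

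*Combined protocol and SAP*

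**What the plan says.** The unit of the primary outcome differs by section:

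- **Notification.** Section 8.1: "The denominator is the total number of DOAC prescription notifications", whether routed to the prescriber or to the pharmacist. The synopsis (1.1) and the endpoint table (section 3) also express the endpoint as a proportion of notifications.
- **Prescription.** Section 9.3.2 takes the proportion "among all prescriptions that triggered a notification".
- **Patient.** Section 9.3.1 will "compare the proportion of patients receiving an evidence-based DOAC prescription within seven business days following the notification", using a mixed-effects logistic model for a "binary patient-level outcome variable of evidence-based DOAC receipt after an alert" with a prescriber random effect. Section 9.1 powers the comparison on 600 patients.
- **Prescriber-patient pair.** Section 9.3.5 (sensitivity analyses) describes the primary analyses as "intent-to-treat analyses among prescriber-patient dyads for whom an alert was triggered".

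The alert outcome has the same split: alerts in 8.1, prescriptions in 9.3.3, patients in 9.3.1.

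On firing, section 6.1.1 says "Existing prescription notifications are triggered once daily through an EHR registry that is updated continuously". The synopsis and section 2.1 link a notification to the appearance of a new problem. Section 8.2 plans to count how often a notification is opened before anyone responds to it. The schedule of activities (1.3) collects data at later alerts and notifications as well as the first. No section gives a first-notification, episode or de-duplication rule.

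**The concern.** Two analysts could build different primary datasets from this plan, each with a section to cite. The choice has no effect while every patient has exactly one notification. Once some patients have more, a per-notification proportion weights each patient by the number of notifications received. That number accrues after randomisation and may depend on how well the assigned routing works, because an arm that resolves errors sooner or more fully may generate fewer later records. The per-notification difference between arms can then depart from the per-patient difference for which the trial was sized. The declared primary endpoint would be one quantity and the power statement would describe another.

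**Working it through.** **1. Which unit the power statement uses.** Inputs from section 9.1: 150 prescribers per arm, 2 patients each, ICC 0.1, alpha 0.05, 40% versus 52%. Sidedness is not stated for the primary comparison; two-sided is assumed, as stated for the moderator analyses.

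- Design effect = 1 + (2 − 1) × 0.1 = 1.1
- Effective n per arm = 300 / 1.1 = 272.7
- Standard error under the null = √(2 × 0.46 × 0.54 / 272.7) = 0.0427; under the alternative = √((0.24 + 0.2496) / 272.7) = 0.0424
- Power = Φ((0.12 − 1.96 × 0.0427) / 0.0424) = 80.5%, against the stated 80%

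The stated figure is therefore the one-outcome-per-patient calculation with clustering by prescriber. (Table 3 prints 63% for the same case: 2 patients, base 0.4, risk ratio 1.3. The recomputation supports the text, not that cell; this is a separate matter.)

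**2. When the units differ.** Let n be a patient's number of notifications and y the share of them followed by a change. Across the patients in an arm:

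per-notification proportion = Σ(n·y) / Σn = mean(y) + Cov(n, y) / mean(n)

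If n = 1 for everyone, the second term is zero and the definitions coincide. If n varies and is related to success, the proportion shifts, by an amount that can differ between arms.

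**3. Illustration only.** The re-notification rules below are assumptions; none is in the documents. Suppose 40% and 52% of errors are changed within 7 days, with change days uniform over days 1 to 7, and the rest stay unchanged. With k the mean number of notifications for a changed error and F the number for an unchanged one, the per-notification proportion is p·k / (p·k + (1 − p)·F).

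| Assumed rule | k | F | Records per error | Per notification | Difference |
|---|---|---|---|---|---|
| One notification per error | 1 | 1 | 1 vs 1 | 0.40 vs 0.52 | 0.120 |
| Every 7 days for 15 days | 1 | 3 | 2.20 vs 1.96 | 0.18 vs 0.27 | 0.083 |
| Daily for 15 days | 4 | 15 | 10.60 vs 9.28 | 0.15 vs 0.22 | 0.073 |
| Daily for 30 days | 4 | 30 | 19.60 vs 16.48 | 0.08 vs 0.13 | 0.045 |

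Worked for the second row: 0.40 / (0.40 + 0.60 × 3) = 0.40 / 2.20 = 0.182, and 0.52 / (0.52 + 0.48 × 3) = 0.52 / 1.96 = 0.265.

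The departure is not inevitable even with repeats. If each open error has a constant daily chance of being changed, every notification has the same 7-day success probability and the result stays at 0.40 versus 0.52.

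**4. Effect on power in the same illustration.** Simulated with variance clustered by prescriber, power per patient versus per notification was 80.6% vs 80.3% (weekly for 15 days), 80.6% vs 74.4% (daily for 15 days) and 80.2% vs 72.8% (daily for 30 days).

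**The case against.** The strongest reply is that the unit is largely settled: the model, the power calculation and the prescriber-patient wording in 9.3.5 all point to about one record per patient, and 8.1 is loose phrasing. Much of this stands, and it is why the fix should adopt the patient unit. But 8.1 states an explicit denominator, 9.3.2 states another, and neither the patient nor the pair wording says which notification is scored when there are two.

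Two stronger readings are tempting, and the documents support neither.

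- **That an unresolved error is counted again every day.** Daily triggering can equally mean a daily registry run that sends only newly detected errors. The synopsis and section 2.1 tie a notification to something new, section 8.2 treats it as one message that may be opened several times, and the note in section 1.2 returns errors to the pharmacist dashboard after 15 days. Re-notification is an open question, not a documented feature. What remains without it is narrower: a patient with two separate new errors, at a frequency the documents do not give.
- **That the lack of a patient-level random effect invalidates the test.** Assignment is by prescriber, and a fitted prescriber effect estimates its own variance; it is not held at ICC 0.1. With 2 patients × 2 records, within-patient correlation w and between-patient correlation 0.1, the average within-prescriber correlation is (w + 0.2) / 3. The exchangeable design effect is 1 + 3 × (w + 0.2) / 3 = 1.2 + w, identical to the direct value 1 + w + 2 × 0.1. In the simulation above, the per-notification type I error with prescriber-clustered variance was 4.2% to 5.7%.

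**Conclusion.** The point holds as an inconsistency in the definition of the primary outcome and, in the same form, of the alert outcome. The plan names several units, powers only the per-patient one, and gives no rule for a patient with more than one notification. Its numerical effect is unknown. It is zero if no patient has repeats; under the assumed re-notification rules, the 12-point per-patient difference becomes 4.5 to 8.3 points per notification, or stays at 12 under a constant daily chance of change. Those figures show direction and possible scale and are not estimates for this trial. There is no finding here that the trial is underpowered or that its type I error is inflated. It should be corrected before unblinded data are seen.

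**What to change.** In sections 1.1, 3, 8.1, 9.3.1, 9.3.2 and 9.3.3, use one primary unit that matches the model and the power calculation: the first notification (or first alert) for each patient within prescriber, scored once for any prescription change within the window. State whether an unresolved error generates a further notification. Keep all notifications, or all separate error episodes, as a sensitivity analysis with prescriber-clustered inference, and report the number of notifications per patient by arm.

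The cost is wording and one de-duplication step. Sample size and stated power are unchanged, because they were computed for this unit. The downside is slightly fewer records in the primary analysis if repeats occur; later separate errors would inform only the sensitivity analysis.
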